3.2 Randomization

A blocked randomization scheme with a block size of 4 (ratio of 3:1 of active:placebo) that is stratified by site will be used. Site-specific randomization lists will be provided to the Production manager (unblinded personnel) prior to any subjects being randomized.

For each subject, at Visit 3, one week before bone marrow aspiration (BMA), the clinical site will notify the cell culture facility of the eligibility of a subject; the cell production facility personnel will then sequentially assign a randomization number according to the randomization list for each site.

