5 Blood Biochemistry: Na, K, Cl, HCO₃, BUN, Cr, Glucose, Ca, Mg, Phosphorus, total protein, triglycerides (TG), Total cholesterol, HDL, LDL, urea, creatinine, total bilirubin, AST(GOT), ALT(GPT), ALP - Time Window: +/- 2 hours

6 Urinalysis (dip-stick test) - Specific Gravity, pH, glucose, protein, ketones, blood

7 Coagulation PT, PTT

8 Can be done prior to discharge

4. Study Treatment

The investigational products for this study will be

- MSC-NTF cells
- Placebo (Dulbecco Modified Eagle Medium, DMEM)

IT Transplant Procedure: Participants will undergo a lumbar puncture (Spinal needle 20GA 3.50 IN (0.9 x 90 mm)) followed by intrathecal injection of cells or placebo (DMEM).

IM Transplant Procedure: Participants will undergo a unilateral (right) IM transplantation of cells or placebo solution (DMEM) into 24 sites in the upper arm.

The study flowchart described above is shown in Figure 2.

[figure not shown]

Figure 2: Study Groups Flowchart

5. Sample Size

This is a Phase II study for which no formal sample size calculation has been performed. The sample size chosen was not based on statistical considerations. The total of 36 treatment and 12 placebo subjects are expected to be a sufficient number to obtain adequate characterization of common treatment emergent adverse events and to observe trends for treatment effects on the efficacy measures chosen for this study. Additionally, with 36 subjects in the MSC-NTF treatment group, the study has 95% probability of seeing adverse events that occur at a true rate of 8% or greater. Therefore, if an adverse event of a specific type does not occur, there is 95% probability that the true rate of the adverse event is less than 8%.

6. Analysis Populations

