7.2 Efficacy Endpoints

The efficacy endpoints are the following:

- Revised ALS Functional Rating Scale (ALSFRS-R)
- Slow Vital Capacity (SVC) (as a percent of normal)

[REDACTED]

[REDACTED]

[REDACTED]

[REDACTED]

[REDACTED]

[REDACTED]

8. General Considerations

Summaries for continuous variables will include the sample size, mean, standard deviation, median, minimum, and maximum. Minima and maxima will be reported with the same precision as the raw values; means, standard deviations, and medians will be presented to one additional decimal place than reported in the raw values. Summaries for discrete variables will include frequencies and percentages. All percentages will be rounded to one decimal place (i.e., XX.X%). Differences between treatment groups will be calculated as active – placebo and change from Baseline will be calculated as post-treatment – pre-treatment (OR follow-up visit – Baseline). The Baseline value will be defined as the last non-missing measure prior to initiation of investigational treatment. Additionally, for the pre-transplantation period and Transplantation Visits, change from screening summaries will be calculated as pre-transplantation period/Transplantation Visit minus screening.

All efficacy analyses will use one-sided alpha = 0.10 tests (which corresponds to a 2-sided alpha=0.20 test). The two-sided 80% lower confidence limit will be presented for which the lower bound is the 1-sided 90% confidence limit. In addition, the two-sided 90% and 95% confidence intervals around the difference between treatments as well as two-sided 95% confidence intervals around the point estimates within each treatment group will be provided. All summaries will be presented by treatment.

Statistical programming and analyses will be performed using SAS® Version 9.2 or higher.

[REDACTED]

[REDACTED]

[REDACTED]

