Descriptive statistics on the observed and change from baseline in the ALSFRS-R total score, ALSFRS-R motor score, and SVC will be summarized at each visit, by treatment group. The analyses will be evaluated for the FAS primarily based on available data (no imputation). Figures presenting the mean ALSFRS-R total and motor scores and SVC score over time by treatment group will be presented. Additionally, figures presenting the ALSFRS-R total and motor scores over time, as separate line plots for each subject will be generated. The change from the Screening Visit measure will be summarized for measures during pre-transplantation. The change from Baseline measure will be summarized for measures post-transplantation. The pre-transplantation slope (change in score per month calculated as the difference between the visit date minus the screening date divided by 30.4375) will be estimated from visits prior to transplantation (including the measure pre-transplantation at the transplantation visit). The post-transplantation slope (change in score per month calculated as the difference between the visit date minus the transplantation date divided by 30.4375) will be estimated from visits post transplantation (including the measure pre-transplantation at the transplantation visit). The analysis of change in slope from pre-transplantation to post-transplantation in ALSFRS-R total and motor and in SVC will be estimated using a two-step model. In the first step, linear regressions will be fitted to each subject's pre-transplantation and post-transplantation data separately; and in the 2nd step, the slopes (pre- and post-transplantation slopes) from the first step will be used as a response variable and treatment, period (0 for pre-transplantation slope and 1 for post-transplantation slope), and treatment by period interaction as explanatory variables in a fixed-effects linear model. The two-way interaction between treatment and period will be used to compare the change in slope

in the active treatment group to the change in slope in the placebo group. The post - pre slope estimate within each treatment group will be used to test the change from pre-transplantation to post-transplantation.

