10.2.1 Subgroup analyses

Subgroup analyses will be performed to investigate the consistency of the treatment effects for different groups of subjects.

Subgroup analyses will be conducted for the following endpoints:

- ALSFRS-R total score
- ALSFRS-R motor score
- SVC

Subgroups to be evaluated include the following:

- Baseline SVC:
 - $\geq 70\%$
- Baseline ALSFRS-R total score:
 - < -2 in the change from screening to baseline in ALSFRS-R total score
 - ≥ -2 in the change from screening to baseline in ALSFRS-R total score
- Baseline ALSFRS-R motor score:
 - < -1 in the change from screening to baseline in ALSFRS-R motor score
 - ≥ -1 in the change from screening to baseline in ALSFRS-R motor score

The primary analysis model will be repeated for each level of the subgroups.

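### SAP 10.2.1 asks whether the treatment effect is consistent across subgroups but never estimates the difference in effect between levels

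*SAP*

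**What the plan says.** SAP 10.2.1 states the aim: "Subgroup analyses will be performed to investigate the consistency of the treatment effects for different groups of subjects". It covers ALSFRS-R total, ALSFRS-R motor and SVC. The subgroup factors are baseline SVC, of which only the level of 70% or more appears, and the screening-to-baseline change in ALSFRS-R total score (cut at -2) and in motor score (cut at -1). The method is one sentence: "The primary analysis model will be repeated for each level of the subgroups".

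That model is in SAP 10.2. Each subject's pre- and post-transplantation slopes are the responses, and treatment, period and treatment by period are the explanatory terms: "The two-way interaction between treatment and period will be used to compare the change in slope" between arms. SAP 10.2.2 screens covariates, baseline SVC among them, but mentions no interaction with treatment.

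SAP section 8 sets the general rule: "All efficacy analyses will use one-sided alpha = 0.10 tests". The same paragraph also calls for confidence intervals around the treatment difference. SAP section 5 gives 36 active and 12 placebo subjects and says "The sample size chosen was not based on statistical considerations". SAP 3.2 stratifies randomization by site only.

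**The concern.** Consistency concerns a difference between differences: is the treatment effect on change in slope the same in one level as in the other? Two separate fits give two effects and two tests, but no estimate of how far apart the effects are and no interval for that distance. One significant level beside one non-significant level is not evidence that the effects differ, because each level has a larger standard error than the whole trial.

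The placebo arm has 12 subjects, and nothing in the randomization protects its split across levels. The SAP recognises this fragility elsewhere: section 6.4 drops the per-protocol analysis because of the small sample, the 3:1 ratio and a possible imbalance falling on placebo. The subgroup section has no similar caution. At stake is a chance pattern being taken for a responder group, or real heterogeneity going unmeasured.

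**Working it through.** **The plan's own figure.** The only computed design figure is in SAP section 5: a 95% chance of seeing an adverse event of true rate 8% among 36 subjects. 1 - 0.92^36 = 0.950, which reproduces it. The documents give no power, effect size or SD for efficacy, so the effect sizes below are assumptions.

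**Inputs from the documents.** 36 v 12 (SAP section 5); one-sided alpha 0.10 (SAP section 8); separate fits by level (SAP 10.2.1).

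**Assumed.** Two equal levels of 18 v 6, complete data, and a uniform true effect d in SDs of a subject's change in slope, the same SD in both levels.

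**1. Standard errors (in SD units).**
- Full trial: sqrt(1/36 + 1/12) = 0.333.
- One level: sqrt(1/18 + 1/6) = 0.471, which is 1.41 times larger.

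**2. Discordance with a correct standard error.** Power p per level comes from the noncentral t distribution (22 df, noncentrality d/0.471). P(exactly one level significant) = 2p(1 - p).

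| d | Full-trial power | Power per level | Exactly one significant |
|---|---|---|---|
| 0 | 10% | 10% | 18% |
| 0.5 | 58% | 40% | 48% |
| 0.7 | 79% | 57% | 49% |
| 0.9 | 92% | 72% | 40% |

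For d = 0.7: 2 x 0.570 x 0.430 = 0.490. With a 75/25 split (27 v 9 and 9 v 3), the figures for d = 0.5, 0.7 and 0.9 are 50%, 54% and 50%.

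**3. Discordance under the SAP's second-stage model.** That model has no subject term, so it treats a subject's two slopes as independent. If they correlate positively at rho, the model's standard error is too large by about 1/sqrt(1 - rho), and its tests are conservative. Simulated at 18 v 6 per level:

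| d | rho = 0.5 | rho = 0.7 |
|---|---|---|
| 0 | 7% | 2% |
| 0.5 | 35% | 19% |
| 0.7 | 47% | 32% |
| 0.9 | 50% | 44% |

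**4. Comparing direction only.** If a reader looks only at the sign of the two estimates, they disagree in 30%, 12% and 7% of trials at full-trial power of 50%, 80% and 90%.

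**5. Level sizes.** Six placebo subjects per level is simply 12/2. If a level holds 24 of the 48 subjects, its placebo count has a 95% range of 3 to 9, and there is a 32% chance that one of the two levels has 4 or fewer. The ALSFRS-R total cut may be uneven. The slower decline cited in Protocol 6.3.7, 0.92 points/month, gives 0.92 x 12 x 7/30.4375 = 2.5 points over 12 weeks and 3.4 over 16. With an assumed SD of change of 2 to 4 points, about 50-67% of subjects fall below -2. At the faster cited rate, 2.35 points/month, most do (84% to nearly all).

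**6. What a between-level contrast delivers.** Its standard error is sqrt(2 x (1/18 + 1/6)) = 0.667 SD, twice the overall 0.333. In simulation with a uniform effect and independent slopes, it signals a difference in 10.0% of trials at two-sided 0.10, as it should. If the levels truly differ by 0.708 SD (the effect that gives 80% full-trial power), its power is 28% at two-sided 0.10. A normal 95% interval is about ±1.96 x 0.667 = ±1.3 SD.

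**The case against.** The strongest reply is that SAP 10.2.1 never says consistency will be judged by comparing significance. It states no criterion and makes no responder claim, and the section 8 rule that brings in the 0.10 test also brings in intervals for the treatment difference, so level-specific estimates with intervals are arguably already planned. This stands. The discordance figures describe what happens if a reader compares tests, not a rule the SAP has adopted.

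Second, the 40-49% range is not for the model the SAP specifies. This also stands: positive correlation between slopes lowers discordance at smaller effects, and with no effect it falls from 18% to 2-7%. In addition, the ALSFRS-R cuts are made on a quantity close to the pre-transplantation slope, itself a response in the model, so an equal SD in each level is only an approximation for the matching endpoint.

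Third, a reader might take the single SVC level for an error. The documents do not support that: a second level may have been lost in text extraction or redaction, or the restriction may be deliberate.

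Fourth, efficacy is secondary in a safety study, and the contrast has little power. Both are true. But low power is a reason to report an interval, not to leave the quantity out. None of the four replies supplies the missing between-level estimate.

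**Conclusion.** The gap is real and moderate. The plan names consistency as its aim and provides no estimate of it. Read through level-wise tests, a uniform effect of 0.5 to 0.9 SD would look inconsistent in about 40-49% of trials with a correct standard error, or about 19-50% under the SAP's model with slope correlation of 0.5 to 0.7. These ranges rest on an even 18 v 6 split, complete data and assumed effect sizes. With a correct standard error, the 75/25 split gives 50-54%.

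Three stronger readings go too far. The SAP does not say it will declare subgroups consistent or inconsistent by p-value. It does not state that each level holds about 6 placebo subjects. Nor does it say that subgroup results will set eligibility for a later study: the planned multi-dose study is mentioned in SAP section 16 in connection with the Week 8 slopes only.

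**What to change.** In SAP 10.2.1, for each subgroup factor:

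- Add one FAS model with treatment by period by subgroup and all lower-order terms, respecting the pairing of each subject's two slopes. A simple way is to model each subject's change in slope on treatment, subgroup and their interaction.
- Report the between-level difference in treatment effect with a 95% confidence interval as the consistency result.
- Keep the level-specific estimates and intervals, show arm counts per level, and label them descriptive without significance claims.
- State that a non-significant interaction does not show consistency.
- For SVC, confirm whether a level below 70% is intended. If so, apply the same contrast. Using SVC as a continuous modifier is optional and adds a linearity assumption.

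The cost is a paragraph of SAP text and a few lines of code, with no new data. The drawback is a wide interval, which shows how little 12 placebo subjects can say about subgroup differences.

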10.2.2 Covariate analyses

Covariates such as time since onset of symptoms, blood pressure, weight or BMI, baseline SVC will be evaluated. The primary model will be fitted with each covariate separately. The significant covariates (p-values <0.25) from these univariate models will be used to build a multivariate model. The covariate that is least significant in the multivariate model i.e. highest p-value above 0.20 will be removed one at a time until all remaining covariates in the model are significant at 0.20.

[REDACTED]

[REDACTED]

[REDACTED]

[REDACTED]

[REDACTED]

[REDACTED]

11. Other Measures

Suicidal ideation and behavior is assessed using the Columbia-Suicide Severity Rating Scale (C-SSRS).

The binary responses, yes or no, can be categorized in one of the following:

Category 1 – Wish to be Dead

Category 2 – Non-specific Active Suicidal Thoughts

Category 3 – Active Suicidal Ideation with Any Methods (Not Plan) without Intent to Act

Category 4 – Active Suicidal Ideation with Some Intent to Act, without Specific Plan

Category 5 – Active Suicidal Ideation with Specific Plan and Intent

Category 6 – Preparatory Acts or Behavior

Category 7 – Aborted Attempt

Category 8 – Interrupted Attempt

Category 9 – Actual Attempt (non-fatal)

Category 10 – Suicidal Behavior

The suicidal ideation score is the maximum suicidal ideation category (1-5 on the C-SSRS) present at the assessment. If no ideation is present, the suicidal ideation score is 0.

A “yes” answer at any time during treatment to any one of the five suicidal ideation questions (categories 1-5) on the C-SSRS will be categorized as “Suicidal ideation”. A “yes” answer at any time during treatment to any one of the five suicidal behavior questions (categories 6-10) on the C-SSRS will be categorized as “Suicidal behavior”. A “yes” answer at any time during treatment to any one of the ten suicidal ideation and behavior questions (categories 1-10) on the C-SSRS will be categorized as “Suicidal ideation or behavior”.

Subjects with any suicidal ideation, suicidal behavior, and suicidal ideation or behavior will be tabulated by treatment at screening (lifetime measure), during the pre-transplantation period and during the post-transplantation period; additionally, the maximum number of questions answered yes at any visit for suicidal ideation, suicidal behavior, and suicidal ideation or behavior will be tabulated within each period. Shift tables

showing changes in suicide ideation scores from screening (lifetime measure) to worst on Baseline (pre-transplantation period) and from Baseline to worst post-treatment will also be provided. Data will be reported as available without data imputation.

12. Interim Analyses

There are no interim analyses planned for this study.

13. Deviations from Protocol-Stated Analyses

- [REDACTED]
- [REDACTED]
- [REDACTED]
- Updated mixed linear repeated measures statistical model to be a simple linear regression along with general linear model to compare changes in slopes between treatment groups as described above.
- Added slope analysis for 8-week and 16-week follow-up periods was added for the efficacy endpoints.
- Changed population definitions from the protocol stated definitions by removing analyses on mFAS and PP populations.
- Protocol referred to day of transplantation as Day 0, however in the SAP it is treated as Day 1.
- Changes between the original protocol and Amendment 1 are assumed to not impact any statistical analyses

14. Reporting Conventions

Reporting conventions will adhere when possible to the International Conference on Harmonization (ICH) Guidance E3, "Structure and Content of Clinical Study Reports". All tables and listings will be presented in landscape format. All SAS output for tables and listings will be distributed in PDF files.

15. References

16. SAP Revision History

Section #	Description of Change	Rationale
6	Updated FAS definition and removed mFAS	During the blinded data review it was determined that the difference between the FAS and mFAS was only one subject and hence no analyses would be performed on the mFAS

Section #	Description of Change	Rationale
6	Analysis on PP population is deleted	Due to the small sample size in the study, the 3:1 ratio of randomization between active and placebo and the possibility that a disproportionate number of the subjects may be in the Placebo group, analysis on the PP population will not be performed.
10.2 and 10.3.1	Updated the primary model from mixed-effects linear model to two-step model.	The mixed-effects linear model has restriction on the random effects estimates (slope) which causes the estimated slopes to be either lower or higher than the actual slopes from simple linear regression which was deemed to be more appropriate.
10.2 and 10.3.1	Added slope analysis for 8-week and 16-week follow-up periods	The original analyses of slopes were planned at Weeks 12 and 24, however since only ALSFRS-R is recorded at Week 12 these analyses will also be performed at Week 16. In addition, to determine any shorter term effect of treatment and to assist in design with a planned multi-dose study, analyses of improvement in slopes will also be performed at Week 8.
